## Study Objectives

The goals of this proposed study are to 1) evaluate the potential of using frontal theta-tACS during a cognitive task to mitigate cognitive disturbance in MS, specifically, information processing speed and attention, and 2) understand stimulation response variability at the individual-level. Processing speed and attention will be targeted for remediation due to the prevalence of their decline in MS and our previous research (and others) that show tACS may improve these cognitive functions.

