- **Covariates to be included in Regression Analyses (Specific Aim 2).** Regression analysis will be performed to identify predictors of tACS effects on the primary outcome measures: divided attention and processing speed. Three classes of predictors will be assessed: neuroanatomy, cortical excitability, and clinical severity, in addition to those typically accounted for in MS studies: demographic (age, gender, education) and clinical features (MS duration, EDSS). 1) **Neuroanatomy.** Differences in the thickness of the skull, cerebrospinal fluid, subcutaneous fat, as well as gyral pattern, and local tissue heterogeneities (such as atrophy) yield differences in resistivity that will differentially impede current flow to cortex (Opitz, Paulus, Will, Antunes, & Thielscher, 2015; Shahid, Wen, & Ahfock, 2013; Truong, Magerowski, Blackburn, Bikson, & Alonso-Alonso, 2013). The consequence of this anatomical variability can lead to 1.5 to 3-fold differences in the induced electric field in cortex (Datta, Truong, Minhas, Parra, & Bikson, 2012; Russell et al., 2013), contributing to variable tES outcomes. Indeed, we have recently demonstrated that the amount of current that reaches the brain predicts tACS efficacy (Preliminary Study 1). Therefore, to assess the amount of tACS-induced current that reaches the brain, individual MRI data will be used to model the electric field within each patient's brain. Standard modeling software will be used for this task (Huang, Datta, Bikson, & Parra, 2019). As patients' annual clinically-acquired brain MRIs are available in [name] BRIDGE platform (bridge.ucsf.edu), funds are not requested to collect MRI data. The average modeled electric field magnitude within the PFC will be used as a predictor variable for the regression analysis. 2) **Cortical excitability.** Evoked potentials (EPs) from the single task version of the discrimination task will be used to assess cortical excitability as a predictor variable in the regression analysis. In MS, demyelination and axonal loss occur, which not only changes the current flow of tES, but alters cortical excitability as measured by EPs (Caramia et al., 2004). EP abnormalities in MS include morphological changes, delayed latencies, wave cancellation and increased refractory period (Iodice et al., 2016). Importantly, baseline cortical excitability, as measured by EPs, has been shown to be a significant covariate associated with variable effects of tES across individuals (Jamil et al., 2017). 3) **Clinical severity.** In a meta-analysis of non-invasive neurostimulation effects, we have shown that patients with the greatest clinical severity are the ones who benefit most from neurostimulation ([name], Ku, [name], & [name], 2015). Here, we will use the MS Functional Composite 4 (MSFC4) as a metric of clinical severity and assess it as a predictor variable in the regression analysis. The MSFC4 assesses four key MS-related functional domains: ambulation (timed 25 foot walk), upper extremity dexterity (9-

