### **Interventions (Sessions 2 – 4).**

○ **Transcranial alternating current stimulation (tACS).** TACS will be applied at 6 Hz for the Verum tACS group and 1 Hz tACS for the Frequency Control group because higher frequencies of stimulation (above theta) may introduce visual flickering (or phosphenes) that could confound the interpretation of the data (Paulus, 2010; Schutter & Hortensius, 2010). Moreover, 1-Hz tACS has not been associated with cognitive alterations (Antal et al., 2008; Castillo Saavedra et al., 2014) and we have verified its use as a control in Preliminary Study 1. A sinusoidal alternating current of 1mA peak amplitude (2mA peak-to-peak amplitude) will be delivered via a pair of Ag/AgCl electrodes ( $3.14\text{ cm}^2$ ) through a Starstim-32 device (Neuroelectrics, Spain) while patients are engaged in a tablet-based cognitive task (EVO, see below). During each session, participants will receive 20 min of stimulation with a 15-s ramp up and 15-s ramp down. The stimulation electrodes will be located at F3 and F4 of the 10–20 electrode coordinate system (above PFC). Impedance will be kept below 10 kΩ. In order to confirm that the frequency control was an appropriately blinded manipulation and all patients tolerate tACS well, all patients will be asked to complete a 1-min survey to scale the perception of stimulation (headache, scalp pain, tingling, burning sensation) from 1 (mild) to 10 (severe) at the end of each session. If the score on the stimulation perception survey is below 4 for each item, tACS will be considered well-tolerated.

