○ **Cognitive paradigm.** During tACS, participants will be engaged in a divided attention paradigm known as EVO (Akili Labs, Boston) (Anguera et al., 2017; Anguera, Jordan, Castaneda, [name], & Arean, 2016; Arean et al., 2016; Davis, Bower, & Kollins, 2018). The EVO paradigm consists of a divided attention paradigm that combines visuomotor tracking and perceptual discrimination tasks similar to, but distinct from, those used for our outcome measure of divided attention. EVO utilizes adaptive algorithms to change game difficulty on a trial-by-trial basis for both the perceptual discrimination (adapting the response window for a target) and visuomotor tracking (adapting the speed of the forward path and sensitivity of the user's motions), with real-time feedback making the patients aware of their performance. More specifically, the adaptive algorithm makes proportional changes in gameplay difficulty when the participant's performance deviates from an 80% accuracy median, which ensures that task difficulty is equated across participants and enhances participant engagement so that the paradigm is never too easy (or boring) nor too difficult (or frustrating). Each task lasts approximately 4 minutes, with 7 task runs comprising one session (experimental day). As the

patients improve their performance throughout gameplay, they are transported to different visual “worlds” in the EVO universe, meant to immerse the participant and enhance the depth of engagement and compliance. Audio and visual cues are continuously available to the participant so they are given feedback as to their performance. Since the adaptive mechanics strive to keep the participant at ~80% accuracy, the participant is challenged to constantly improve upon their own cognitive control performance in order to reach the next level.

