- **Preliminary study 2.** We have recently demonstrated the utility of the proposed experimental paradigm (i.e. EVO) and the proposed processing speed outcome measure in people with MS. Specifically, in a behavioral intervention study, MS patients who played EVO improved information processing speed ( $p=0.003$ ) ([name] et al., 2019). In a follow-up randomized controlled pilot trial, the mean increase in SDMT was 6.10 for EVO task group compared with 3.55 for an active control group, with clinically improvement significantly more likely to be retained for at least two months in the EVO group ([name] et al., 2019). *These preliminary results provide additional support for the feasibility of using the proposed experimental paradigm in MS and the selection of outcome measures for Specific Aim 1.* In this preliminary study, we also demonstrated that SDMT improvement was found to be associated with clinical severity, which revealed that clinical data contributes to the change of SDMT scores. This shows that, *given the heterogeneity of MS, understanding individual variability is critical for clinical trials assessing cognitive function interventions in MS, and underscores the importance of Specific Aim 2* ([name] et al., 2019).

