**Secondary outcome measure: Frontal theta power.** Results from Preliminary Study 1 also showed that the Verum tACS group, and not control tACS, exhibited a correlation between divided attention and frontal theta power such that those participants with the greatest increase in frontal theta power yielded the greatest improvement in divided attention ability ( $r = 0.50$ ,  $p = 0.04$ ). Here, it is hypothesized that MS patients who receive Verum tACS will exhibit similar neuroplastic changes in frontal theta activity. To test this, frontal theta power will be extracted during the discrimination task (theta dual task minus theta single task) and a change score will be calculated (post-tACS minus pre-tACS). A regression analysis will be conducted between theta power and the change in the divided attention index (post-tACS minus pre-tACS) described above. It is expected that increases in theta power only the Verum tACS group will be related to improvements in divided attention ability. To further characterize between group differences, theta power will be submitted to an ANCOVA with Group (Verum, Control) and Session (pre-tACS, post-tACS) as factors. Although age will be matched across groups, age will serve as the covariate to account for within-group differences. A Group x Session interaction is expected to show that the Verum tACS group, compared to the control group, will exhibit a larger increase in theta power post-tACS, indicating enhanced neuroplasticity. For this interaction, 20 participants per group will yield  $>95\%$  power ( $1-\beta$ ) at a 95% significance level ( $1-\alpha$ ) with an expected effect size of  $f = 0.28$ .

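### The Aim 2 regression for predictors of tACS effects names no Group x predictor term; on the listed terms alone it cannot separate response to 6 Hz stimulation from training or practice gain

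*Combined protocol and SAP*

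**What the plan says.** Study Objectives gives two goals, and the second is to "understand stimulation response variability at the individual-level". The only description of the analysis for that goal is the item on covariates for the regression analyses (Specific Aim 2), under Outcome measures: "Regression analysis will be performed to identify predictors of tACS effects on the primary outcome measures: divided attention and processing speed". It names three classes of predictor: mean modelled electric field in the prefrontal cortex, evoked potentials from the single-task discrimination task, and MSFC4. It adds age, gender, education, MS duration and EDSS. It does not state the dependent variable, whether one or both arms enter, a Group term, or a Group x predictor term. Statistical Design and Power covers the two primary outcomes and frontal theta power, and contains no paragraph on Aim 2.

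On the interventions: "TACS will be applied at 6 Hz for the Verum tACS group and 1 Hz tACS for the Frequency Control group", and "During tACS, participants will be engaged in a divided attention paradigm known as EVO". So the arms differ in stimulation frequency and share the training task.

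Preliminary study 2, described without any stimulation, reports that "the mean increase in SDMT was 6.10 for EVO task group compared with 3.55 for an active control group", and that "SDMT improvement was found to be associated with clinical severity, which revealed that clinical data contributes to the change of SDMT scores". No scale, direction or size is given for the second statement.

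For the secondary outcome, Statistical Design and Power plans a regression of the change in divided attention on theta power, and comments: "It is expected that increases in theta power only the Verum tACS group will be related to improvements in divided attention ability". A Group x Session ANCOVA on theta power follows. No comparison of the theta–attention slopes between groups is stated.

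**The concern.** A predictor of response to 6 Hz stimulation is a factor across which the difference between 6 Hz and 1 Hz changes. A factor that predicts how much a patient gains from three EVO sessions, or from a second sitting of the same test, is something else, and it would appear in either arm. A regression within the Verum arm, or on both arms pooled without an interaction, estimates a blend of the two.

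This matters most for severity and SDMT. The pilot work already links severity to SDMT gain without stimulation, and the plan then puts MSFC4 forward as a candidate predictor of the tACS effect on SDMT. A repeat of the pilot association could be reported as evidence about who responds to tACS. That is one of the study's two goals, and such a result could steer patient selection in a later trial. The 1 Hz arm allows the two to be separated, but the plan does not say that it will be used for this.

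The theta analysis has the same gap: a relation expected in one group only needs a test that the two slopes differ.

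**Working it through.** **No figure to reproduce.** The documents give no power, sample size or correlation for the Aim 2 predictors. The correlations below are assumptions.

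**What each model estimates.** Let x be a predictor, γ its slope on training or practice gain (shared by both arms), and δ the extra slope under 6 Hz.

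- Control: change = a + γx + error
- Verum: change = a + Δ + (γ + δ)x + error
- Verum-only regression estimates γ + δ.
- Pooled regression with 20 per arm estimates about γ + δ/2.
- The Group x predictor coefficient estimates δ.

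Adding Group as a main effect removes Δ and leaves γ in the slope. As a check, with a slope of 0.577 in Verum and 0 in Control, the simulated pooled slope averaged 0.29, and 0.577/2 = 0.29.

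**Inputs.** There are 20 patients per arm, 40 in total (Statistical Design and Power). The listed terms number 3 + 5 = 8 if evoked potentials enter as one measure. They number 2 + 4 + 5 = 11 if P1 and N1 amplitude and latency all enter. Data are normal, tests two-sided at 0.05, with 20,000 simulated runs.

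**How often a factor with δ = 0 is flagged.** The factor has the same correlation r with change in both arms. Ranges run over 8 to 11 terms. The collinear rows set the MSFC4–EDSS correlation at 0.5–0.7, with both related to change.

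| Assumption | Verum only (n = 20) | Pooled (n = 40) | Group x predictor |
|---|---|---|---|
| r = 0.5, independent covariates | 32–44% | 83–86% | 5% |
| r = 0.5, MSFC4 and EDSS collinear | 10–20% | 26–48% | 5% |
| r = 0.3, independent covariates | 13–16% | 37–40% | 5% |
| r = 0.3, MSFC4 and EDSS collinear | 7–9% | 11–17% | 5% |

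Single figures of about 84% pooled and 42% Verum-only represent the first row. In a separate 5,000-run check of the pooled model with 8 terms and r = 0.5, the rate was 83.9% without Group and 85.1% with Group as a main effect only. Opposite slopes in the two arms (0.577 and −0.577) were flagged 7% of the time when pooled and 85% by the interaction.

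**Power of the interaction test.** The model is baseline, age, Group, predictor and Group x predictor, with r in Verum and 0 in Control.

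| Variance assumption | r = 0.5 | Verum r for 80% power |
|---|---|---|
| Equal total variance of change in both arms | 32–34% | about 0.82–0.83 |
| Equal residual variance in both arms | 37% | about 0.71–0.72 |

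Under equal total variance, also adjusting for gender, education, MS duration and EDSS lowers the r = 0.5 figure to 29–30%. The 95% interval for the slope difference then has a half-width of about 0.60–0.70 SD of change per SD of predictor. A closed-form noncentral F gives a more favourable 43%: b = 0.5/√(1 − 0.25) = 0.577 and λ = b² × 20/2 = 3.33, on 36 df. It is optimistic because it treats the sample variance of the predictor as known.

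**Theta.** Suppose both arms share the r = 0.50 that the plan quotes for Verum. With 20 per arm, each arm's test is significant with probability about 0.65. If each arm were tested separately at 0.05, the pattern of Verum significant and Control not would arise with probability 0.65 × 0.35 = 0.23. A Group x theta-change test would be significant about 5% of the time.

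**The case against.** The strongest reply is that this argues from silence. The Aim 2 text lists covariates and is not a full model: it omits the dependent variable as well as Group. Its target is worded as an effect of tACS, in a trial whose primary tests are all Group x Session. A between-arm contrast is not written, but neither is it excluded. That stands. A reader might infer that the plan has chosen a Verum-only or pooled regression; the documents do not say so.

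Second, the documentary support is narrow. A reader might take the SDMT gains of 6.10 and 3.55 as proof of confounding. They are means, and a gain common to all patients goes into the intercept; only gain that varies with the predictor can mislead. The one sentence that bears on this links severity to SDMT. Nothing comparable is documented for electric field, evoked potentials or divided attention, and Preliminary study 1 reports a correlation of electric field with tACS effects. The EVO course in the pilot was also described as longitudinal, so its sizes may not carry over to three sessions.

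Third, the flag rates depend on assumed correlations and run from 7% to 86%. That also stands. The direction of the problem comes from the algebra and does not depend on them.

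Fourth, the theta section does not say that each arm will be tested separately, so the 23% holds only if that is done.

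Finally, the interaction test would miss a true r = 0.5 factor about two times in three. That is a reason to report intervals and arm-specific slopes. It does not make a model that answers a different question acceptable.

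**Conclusion.** The concern holds as a gap in specification with a definite consequence. Fitted on the listed terms alone, the Aim 2 regression would not distinguish a predictor of 6 Hz response from a predictor of training or practice gain, whether it used the Verum arm or both arms pooled. The data that would separate them come from the design, but their use is not planned.

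The size is illustrative. For an equal correlation of 0.5 in both arms and independent covariates, the false attribution rate is about 84% pooled or 42% Verum-only, against 5% for the interaction. It is much lower for weaker correlations or when MSFC4 and EDSS overlap. The case is documented for severity with SDMT, one of the six predictor–outcome pairs; for the others it is logical only.

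Two further readings go too far. The chance of some false flag when no factor predicts anything (23–26% over three predictors and two outcomes) is not caused by the missing term, because six interaction tests carry 25–26%. And the primary Group x Session comparisons are not touched.

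**What to change.** State the Aim 2 model before unblinding:

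- Analyse both arms. For each primary outcome, fit Group, predictor and Group x predictor for mean prefrontal electric field, one pre-specified evoked-potential measure, and MSFC4. Either the change score or the post score adjusted for baseline will serve. The other listed covariates may stay as adjustment terms.
- Base any claim about a predictor of tACS response, meaning 6 Hz versus 1 Hz, on the interaction estimate with its 95% confidence interval. Report the arm-specific slopes with intervals beside it.
- Label Aim 2 hypothesis-generating and state the power limit: about 32–37% for r = 0.5 against 0, with 80% needing a Verum correlation of about 0.72 to 0.83 depending on the variance assumption. Multiplicity adjustment over the six tests is optional under that label.
- Add Group and Group x theta-change terms to the theta regression, so that the Verum-only expectation is tested directly and not by comparing significance between arms.

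The cost is a few sentences of analysis plan and a little programming. No extra patients are needed. No extra measurements are needed either, provided the planned predictors are obtained in both arms; nothing in the plan restricts them to Verum. The price is low power and wide intervals, which should be stated openly.

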### **Interventions (Sessions 2 – 4).**

○ **Transcranial alternating current stimulation (tACS).** TACS will be applied at 6 Hz for the Verum tACS group and 1 Hz tACS for the Frequency Control group because higher frequencies of stimulation (above theta) may introduce visual flickering (or phosphenes) that could confound the interpretation of the data (Paulus, 2010; Schutter & Hortensius, 2010). Moreover, 1-Hz tACS has not been associated with cognitive alterations (Antal et al., 2008; Castillo Saavedra et al., 2014) and we have verified its use as a control in Preliminary Study 1. A sinusoidal alternating current of 1mA peak amplitude (2mA peak-to-peak amplitude) will be delivered via a pair of Ag/AgCl electrodes ( $3.14\text{ cm}^2$ ) through a Starstim-32 device (Neuroelectrics, Spain) while patients are engaged in a tablet-based cognitive task (EVO, see below). During each session, participants will receive 20 min of stimulation with a 15-s ramp up and 15-s ramp down. The stimulation electrodes will be located at F3 and F4 of the 10–20 electrode coordinate system (above PFC). Impedance will be kept below 10 kΩ. In order to confirm that the frequency control was an appropriately blinded manipulation and all patients tolerate tACS well, all patients will be asked to complete a 1-min survey to scale the perception of stimulation (headache, scalp pain, tingling, burning sensation) from 1 (mild) to 10 (severe) at the end of each session. If the score on the stimulation perception survey is below 4 for each item, tACS will be considered well-tolerated.

○ **Cognitive paradigm.** During tACS, participants will be engaged in a divided attention paradigm known as EVO (Akili Labs, Boston) (Anguera et al., 2017; Anguera, Jordan, Castaneda, [name], & Arean, 2016; Arean et al., 2016; Davis, Bower, & Kollins, 2018). The EVO paradigm consists of a divided attention paradigm that combines visuomotor tracking and perceptual discrimination tasks similar to, but distinct from, those used for our outcome measure of divided attention. EVO utilizes adaptive algorithms to change game difficulty on a trial-by-trial basis for both the perceptual discrimination (adapting the response window for a target) and visuomotor tracking (adapting the speed of the forward path and sensitivity of the user's motions), with real-time feedback making the patients aware of their performance. More specifically, the adaptive algorithm makes proportional changes in gameplay difficulty when the participant's performance deviates from an 80% accuracy median, which ensures that task difficulty is equated across participants and enhances participant engagement so that the paradigm is never too easy (or boring) nor too difficult (or frustrating). Each task lasts approximately 4 minutes, with 7 task runs comprising one session (experimental day). As the

patients improve their performance throughout gameplay, they are transported to different visual “worlds” in the EVO universe, meant to immerse the participant and enhance the depth of engagement and compliance. Audio and visual cues are continuously available to the participant so they are given feedback as to their performance. Since the adaptive mechanics strive to keep the participant at ~80% accuracy, the participant is challenged to constantly improve upon their own cognitive control performance in order to reach the next level.

Using this cognitive paradigm, we have previously demonstrated that frontal theta activity is related to divided attention processes (Anguera et al., 2013). Importantly, because tACS can help entrain intrinsic neural oscillations during task performance, Preliminary Study 1 demonstrated that theta tACS during this cognitive paradigm improves divided attention abilities more so than control stimulation. Furthermore, Preliminary Study 2 has shown that a longitudinal intervention with EVO in MS patients improves processing speed. Together, these Preliminary Studies provide confidence that tACS will enhance divided attention and processing speed in MS patients through the entrainment of frontal theta oscillations that are inherent to EVO task performance.

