**Fig 1. Structure of the experiments**

experiment is proposed to assess whether tACS may yield improvements in divided attention and information processing speed in MS (Specific Aim 1) and identify predictive factors of response to tACS (Specific Aim 2). The experimental paradigm consists of 5 daily sessions (conducted over up to 10 days) (Fig 1). During session 1 (baseline; pre-tACS) and session 5 (follow-up; post-tACS), participants will be assessed on divided attention while electroencephalography (EEG) data is acquired. EEG data will enable assessments of neuroplastic changes associated with tACS effects on divided attention and it will also serve to quantify cortical excitability as a predictor for tACS effects. Additionally, processing speed will be assessed along with questionnaires on pain and fatigue. During sessions 2-4, tACS will be applied while participants are engaged in a tablet-based multitasking task, which includes divided attention and processing speed components, but is distinct from the primary outcome measures.

**Inclusion/Exclusion Criteria.** Inclusion Criteria: age 18-65, diagnosis of MS (relapsing or progressive) according to McDonald criteria (Polman et al., 2011), Expanded Disability Status Scale (EDSS)≤6.5 (Noseworthy et al., 1990), no paresis of the upper limbs, a minimum of 3 months since the last relapse, no severe depression (Beck Depression Inventory<19), normal hearing, and no changes in MS or symptomatic medications in past 2 months. Exclusion Criteria: prior brain surgery, clips in brain, epilepsy or other neurological or non-affective psychiatric disorders, pregnancy.

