**c. Potential Risks:**

- **Electroencephalography:** There are no known risks associated with EEG procedures, all of which have been used extensively in previous research. Conventional EEG recording and sensory stimulation techniques with standard subject grounding procedures are always employed. Some electrode paste may remain on the scalp, but it can be easily removed with shampooing.
- **Transcranial alternating current stimulation:** Although uncommon, tACS has some risk for headache, dizziness, nausea, itchy sensation, irritation under the area of the electrodes and the sensation of shock. TACS has also been reported to cause brief flashes of light ("phosphenes") in humans, but these are not discomforting. Should an adverse effect occur in a participant, that participant will be excluded from continuing the intervention. The protocol described here uses stimulation levels that fall well within safety limits established by basic research investigating neural tissue damage and other possible physiological effects in both humans and animals. Overall, tACS is generally considered a safe, noninvasive and painless technique for modulating neural excitability.

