or less) will be used in the proposed studies, and research utilizing similar stimulation parameters as proposed here have reported no adverse mental or health effects lasting longer than the testing session in normal healthy subjects. Much care will be taken to ensure that stimulation parameters are within the range of published safety guidelines. Although no cases of seizures have been reported using tACS with the proposed stimulation parameters, participants will be screened for past occurrence of seizure and a family history of epilepsy as part of the inclusion/exclusion process. Participants will be fully informed of all procedures and the known and potential risks associated with tACS. Trained personnel will be present during all experimental procedures and all research staff are required to maintain current CPR certification. Drs. [name] (PI), [name] (co-PI), [name] (co-investigator) and [name] (co-investigator) will distinguish between a serious adverse event from a non-serious adverse event and an unanticipated problem. In response to an adverse event, [name], a board-certified neurologist at the UCSF Multiple Sclerosis Center, will monitor participants until they are either deemed fit to go home or are directed to the UCSF Medical Center for additional care. In over 33,000 sessions with over 1,000 participants using stimulation similar to the proposed protocol, there is no evidence for irreversible injury produced by transcranial electrical stimulation (tES) protocols within a wide range of stimulation parameters ( $\leq 40$  min,  $\leq 4$  mA). This includes a wide variety of participants, including persons from potentially vulnerable populations. The analysis consolidates and adds to existing evidence on tES safety and facilitates further research of tES in human subjects (Bikson et al., 2016). A more recent review article suggested that safety is established for low-intensity conventional tES defined as  $<4$  mA, up to 60 min duration per day. Using tACS stimulation, fewer adverse effects were reported compared to tDCS. In specific paradigms with amplitudes of up to 10 mA, frequencies in the kHz range appear to be safe (Antal et al., 2017).

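### Apart from two exploratory scales at session 5, nothing actively asks about adverse effects that begin or persist after a stimulation session, so their detection rests largely on spontaneous report

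*Combined protocol and SAP*

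**What the plan says.** In the combined protocol and SAP, the section on interventions for sessions 2 to 4 describes one side-effect instrument: "all patients will be asked to complete a 1-min survey to scale the perception of stimulation". Its purpose is stated as "In order to confirm that the frequency control was an appropriately blinded manipulation and all patients tolerate tACS well". Four sensations ("headache, scalp pain, tingling, burning sensation") are scored "from 1 (mild) to 10 (severe) at the end of each session", and scores below 4 on every item count as good tolerability.

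Under Potential Risks, the protocol lists headache, dizziness, nausea, itching, irritation under the electrodes and a feeling of shock, and then phosphenes. It adds: "Should an adverse effect occur in a participant, that participant will be excluded from continuing the intervention".

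The section on adequacy of protection places participants under supervision while the experiments run and stops tACS if it becomes painful. After an adverse event, a neurologist monitors the participant until they can go home or are sent on for further care. It also says that studies with similar stimulation settings "have reported no adverse mental or health effects lasting longer than the testing session in normal healthy subjects".

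On timing, Study Design says: "The experimental paradigm consists of 5 daily sessions (conducted over up to 10 days". Pain (Brief Pain Inventory, BPI) and fatigue (Modified Fatigue Impact Scale, MFIS) are collected at sessions 1 and 5 as exploratory measures.

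**The concern.** Every described safeguard works while the participant is on site. No call, diary, start-of-visit question or session 5 adverse-event form is described for the time between visits. An effect that starts at home, or starts on site and continues at home, is therefore likely to reach the record only if the participant raises it.

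Two things are at stake. First, the rule on continuation needs to know whether an adverse effect occurred, and before sessions 3 and 4 nobody is assigned to ask. Second, the tolerability conclusion comes from four sensations scored at the end of a session, so it cannot speak for anything later. This matters more here because the statement that effects do not outlast the session refers to healthy subjects. The covariates section itself says that demyelination and axonal loss in MS change current flow and alter cortical excitability. The trial could supply this information for MS, but its collection schedule is not set up to do so.

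**Working it through.** No power or alpha calculation bears on this point, and the plan gives no figure to reproduce. The check is a comparison of passages plus counting.

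**1. Who is asked what, and when**

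| Time | Stated symptom questions |
|---|---|
| End of sessions 2, 3, 4 | Four-item perception survey |
| Start of sessions 3, 4 | None stated |
| Between visits | None stated |
| Session 5 | BPI and MFIS (exploratory); no adverse-event question |

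The survey is specified for each session. I read that as the stimulation sessions, because it stands under "Interventions (Sessions 2 – 4" and stimulation is given only then. If session 5 were included, the form would still have four items and no look-back.

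**2. Intervals affected**

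- Stimulation exposures: 40 participants x 3 sessions = 120.
- Intervals followed by another stimulation (2 to 3, and 3 to 4): 40 x 2 = 80, or 40 per arm with 20 per group.
- Intervals after the last stimulation (4 to 5): 40 x 1 = 40.

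The continuation rule can act only on the 80. For the other 40 the gap is in recording.

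**3. Longest gap after session 4**

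- Five separate days within 10, for example days 1, 2, 3, 4 and 10: 10 - 4 = 6 days.
- The retention section speaks of five visits over 2 weeks. If that means 14 calendar days: 14 - 4 = 10 days.

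These are maxima. Sessions are described as daily, so a typical gap may be about one day.

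**4. Overlap between named risks and survey items**

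- Named under Potential Risks: headache, dizziness, nausea, itch, irritation, sensation of shock, phosphenes = 7.
- On the survey by name: headache = 1 of 7. Six are not. Tingling and burning may partly stand in for itch or irritation, but nothing on the form corresponds to dizziness or nausea.

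**5. Partial cover**

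- A headache or scalp pain still present at the end of the next stimulation session could be scored then. By that time the stimulation has already been given.
- The session 5 BPI and MFIS, with a session 1 baseline, could show lasting pain or fatigue. Neither covers dizziness, nausea or skin irritation, and neither attributes a symptom to stimulation.

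**6. Two passages that do not share a definition**

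The interventions section treats scores below 4 as good tolerability. The risks section excludes a participant from continuing once an adverse effect occurs, and names headache as a risk. A headache scored 2 would count as tolerated under the first and might count as an adverse effect under the second. The documents do not say which applies.

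**The case against.** A reader might infer that delayed effects are never solicited and that the rule on continuation cannot be triggered by them. The documents do not support that. The rule is not tied to the survey, to time of onset or to how staff learn of the effect, so a participant who mentions a symptom at the next visit can bring it into play. The investigators' task of classifying adverse events is likewise not tied to the survey. The session 5 scales do ask about pain and fatigue. The word never has to go, and cannot becomes depends on spontaneous report.

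A reader might also want to express the gap as a share of clock time observed. Visit length is not stated, so no such share can be derived, and it would not measure how many effects are missed.

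Other objections have some force:

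- The protocol does not say that its listed effects start or persist after the visit, and gives no rate of delayed effects. The number missed is therefore unknown. The protocol's only statement on duration points towards short-lived effects, but it is confined to healthy subjects.
- The wider stimulation record that the protocol cites, over 33,000 sessions including potentially vulnerable people, is reassuring. It concerns irreversible injury, however, not transient symptoms after the visit.
- Consent and contact pages are not in the public text and may ask participants to report symptoms after leaving. That would help, but it would still be reporting on the participant's initiative.
- Safety is not a listed outcome, and no efficacy conclusion changes. This limits the weight of the point. It does not remove it, because the plan does intend to state that tACS is well tolerated.
- More questioning may bring more participants under the existing rule, in a trial of 40 with stated SDMT power of 80%. This is a real cost and belongs with the fix.

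**Conclusion.** The point holds in a limited form. The documents describe no active solicitation of adverse effects that begin or persist after a stimulation session, beyond the exploratory pain and fatigue scales at session 5 and whatever is still felt at the next end-of-session survey. For such effects the continuation rule relies on spontaneous report across 80 participant-intervals. After session 4 the shortfall is in safety recording alone, over a gap of up to 6 days on the 10-day schedule. The planned tolerability statement reaches no further than four sensations at the end of a session.

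This rests on three assumptions: that the survey belongs to sessions 2 to 4, that all 40 participants attend all sessions, and that no look-back procedure exists outside the public text. The number of effects missed cannot be estimated from the documents. Under-counting would be expected in both arms, so the main loss is in absolute frequencies and in the scope of the tolerability claim. The change is worth making because the omission is plain and cheap to close.

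**What to change.** At the start of sessions 3, 4 and 5, before any stimulation or testing:

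1. Ask one open, non-leading question about any symptom since the last session. Record onset, duration, severity and whether it is ongoing.
2. Then go through a checklist of the seven effects named under Potential Risks plus the survey items. With headache on both lists, that is 7 + 4 - 1 = 10 items. Repeating the four survey items alone would miss most of the named risks.
3. Tabulate the answers by arm, alongside the end-of-session scores.
4. Either base the tolerability statement on both time points, or word it as tolerability at the end of the session.

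The below-4 tolerability criterion and the rule on exclusion after an adverse effect must also be reconciled on what counts as an adverse effect. That is for the investigators; no clinical rule is proposed here.

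The cost is about 1-2 minutes at each of three visits that participants already attend, with no new visit and no change to the efficacy analysis plan. More minor symptoms will be recorded, and more participants may come under the existing rule on continuation. The definition should therefore be settled before the question is introduced.
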